Protocol Title

Cognitive Neuroscience of Reward v12.19.18

1) Principal Investigator

[name], Department of Psychology, University of New Mexico
[name] [contact]

IRB Review History

N/A

2) Objectives

The electroencephalographic response known as the Reward Positivity (RewP) is a promising candidate biomarker of diminished valuation in anhedonia. The RewP is only elicited by the presentation of a rewarding outcome and it scales with the central feature of reinforcement learning models, the *positive reward prediction error* (+RPE). Thus, the RewP is specific and sensitive to +RPE, fulfilling the stringent criteria of being an invariant neural marker of this computational process. Importantly, the RewP is boosted by appetitive states and is diminished in depressed individuals, indicating that emotional processes influence this marker of reward learning. While prior work has effectively described these correlations (e.g. Foti and Hajcak, 2009), we do not know how emotion (e.g. depression) and +RPE interact to influence valuation. The objective of this proposal is to test whether mood directly diminishes +RPE coding in the RewP, or if these are separable influences on this signal.

Aim 1: To determine if affect and +RPE have independent or interactive effects on the RewP. Based on our working hypothesis, a sadness manipulation in healthy controls should diminish the RewP. Computational modeling will identify the parameters best associated with the influence of affect on learning, allowing us to capture the richness of these effects in an objective and consistent manner. Statistical modeling will quantify the independent vs. interactive influences of affective and +RPE processes on both the RewP and reward learning.

Aim 2: To determine if anhedonia and +RPE have independent or interactive influences on the source-level generators underlying the RewP. We will use gold-standard source-estimation techniques including concurrent EEG and MEG with MRI-based structural templates and an fMRI-based reward-localizer mask. These tools will be integrated to test our working hypothesis that anhedonia-specific reductions in the M/EEG RewP in depression will co-localize with +RPE in subgenual and ventromedial frontal cortex. This finding will identify a common mechanism for anhedonia-based reductions in reward responsivity.

3) Background

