The RewP is enhanced with positive affective manipulations (Brown & [name], 2018; Threadgill & Gable, 2017) and it scales with self-reported and behavioral reward responsiveness (Bress, Smith, Foti, Klein, & Hajcak, 2012). The RewP is diminished in depressed individuals (Bress et al., 2012; Foti & Hajcak, 2009), particularly a melancholic subtype closely related to anhedonia (Foti, Carlson, Sauder, & Proudfit, 2014; Liu et al., 2014). A reduced RewP is observed in children most vulnerable to depression (Kujawa, Proudfit, & Klein, 2014), and it can predict the probability of a future major depressive episode in never-depressed individuals (Bress, Foti, Kotov, Klein, & Hajcak, 2013). The RewP has good test-retest reliability (Kujawa et al., 2017; Levinson, Speed, Infantolino, & Hajcak, 2017) and internal reliability (Bress, Meyer, & Proudfit, 2015), including reliable diminution due to depressive symptoms (Bress et al., 2015). In sum, these findings demonstrate that the RewP has the sensitivity, specificity, validity, reliability, and prognostic value desired in a biomarker.

However, there is no formal model of the joint sensitivity of the RewP to emotion and +RPE signaling, and thus there is no explanation for the diminishment of this signal in depression. The core problem is that we do not know if emotion influences +RPE coding via the RewP. The statistical interaction of depressed mood and poorer +RPE encoding would identify the RewP as a mechanism of diminished valuation in anhedonia. Conversely, if these are independent influences on the RewP (i.e. main effects), then diminished valuation is likely to be encoded in the downstream targets of the generative area (likely striatum).

The current proposal addresses this hypothesis in separate aims that will manipulate this expression in healthy controls and assess these natural features in anhedonic depressed individuals. This contribution is expected to be significant because it will advance a translational mechanism for deficient valuation in anhedonia.

4) Inclusion and Exclusion Criteria

Inclusion criteria:

- Men or women aged 18-55
- In Aim 2, participants will need to either meet criteria for Major Depressive Disorder via a Structured Clinical Interview for the DSM-5 (SCID), or have an absence of symptoms to qualify as a control.
- Free from psychoactive medication for at least 2 weeks

Exclusion criteria:

- Participants unwilling or unable to give informed consent

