- Presence of other known medical or psychiatric comorbidity that in the investigator's opinion would compromise participation in the study
- For Aim 2, MEG/MRI contraindications
- Any other Axis 1 disorder (unless secondary to depression for depressed group in Aim 2)
- History of psychosis
- Not fluent in English

5) Multi-Site Research

N/A

6) Study Timelines

For Aim 1, individual participant's involvement will last 2-3 hours during 1 day. For Aim 2, individual participant's involvement will last 4-7 hours over 1-2 days. Both aims have a longitudinal component where we will perform a phone interview 3-6 months after the initial assessment. This phone interview consists of a Beck Depression Inventory and is described more in detail in Section 9. We anticipate ongoing enrollment of participants for five years.

7) Study Endpoints

N/A

8) Study Methods

Participants will be asked to complete the following procedures:

Magnetic Resonance Imaging (MRI) scan(s) that may or may not involve simultaneous functional or cognitive tasks. Participants will lie down on a table and be placed into a long donut-shaped magnet. During the scan, participants may be shown pictures and/or words and will be asked to make decisions about the information presented in them. This takes about 1 hour.

Electroencephalograph (EEG) may be done at the same time as the MRI or MEG scan. If so, the participant will wear a cap during the MRI/MEG to record brain waves. Alternatively, the EEG may be performed separately. This takes about 2 hours.

Magnetoencephalography (MEG) records the magnetic activity of the brain at rest and while a person works on a set of tasks. It is performed while sitting in a comfortable chair in a special, magnetically shielded room. MEG does not emit radiation or magnetic fields. Electrodes will be applied to the participant's head and face using a special conductive gel. These will be held in place with a cap or sticky tape. These electrodes are used to monitor brain activity, eye movements, head position, and heartbeat. When the scan is over, all of the electrodes will be removed. This takes about 1 hour of assessment and up to 1 hour of setup.

Neurocognitive testing: In order to examine specific cognitive mechanisms that may be associated with neuropsychiatric disorders, participants will be asked to complete tasks (e.g. remembering letters or numbers, deciding between different monetary options) for up to 2 hours of total testing.

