Participants will be asked to complete one or more of the following questionnaires:

- Demographics (age, gender, race, contact and alternate contact information, etc.)
- Handedness questionnaire
- Beck Depression Inventory (BDI)
- Mood and Anxiety Symptoms Questionnaire (MASQ)
- Behavioral Inhibition / Activation Scales (BIS/BAS)
- Snaith-Hamilton Pleasure Scale (SHAPS)
- Dimensional Anhedonia Rating Scale (DARS)
- Apathy-Motivation Index (AMI)
- Diagnosis information (SCID)

They may refuse to answer any question at any time. These questionnaires may take 2 hours to complete. Direct identifiers will be collected and maintained in the MRN COINS database. All data collected as part of this study will be coded with a Unique Research Subject Identifier (URSI).

Tasks: All tasks are NIMH Research Domain Criteria (RDoC) paradigms that have been previously utilized in studies of depression.

- 1) The Probabilistic Stimulus Selection task (Frank, Seeberger, & O'Reilly R, 2004) will be identical to the PI's previous work ([name] et al., 2010a, 2010b, 2011a, 2011b, 2014). The sophistication of the three separately valued training pairs facilitates a wide range of +RPE values and assessments of reward vs. punishment learning. During training, participants slowly learn to select the optimal item in each pair based solely on probabilistic reinforcement rates. EEG locked to the reinforcing feedback ("correct") elicits the RewP.
- 2) The Probabilistic Rewards task (Pizzagalli, Jahn, & O'Shea, 2005) will be used to assess a commonly-observed decrement in reward learning in depression (Bogdan & Pizzagalli, 2006; Pizzagalli et al., 2005; Vrieze et al., 2013).
- 3) The Gambling task (Foti & Hajcak, 2009) is an extremely rapid assessment (~5 minutes) of neural responses to reward and punishment.
- 4) The Effort Expenditure for Rewards Task (EEfRT: Treadway et al., 2009, 2013) measures a participant's willingness to press buttons over time in order to get reward.

Aim 1 will assess tasks 1,2, and 3 with EEG. Aim 2 will assess task 1 and 2 with MEG and concurrent EEG, task 3 with fMRI, and the 4th task will only be assessed as a behavioral task (no imaging).

Mood and Emotion Manipulations: Mood and emotion manipulation procedures will only be used in Aim 1 (EEG in Logan Hall) and not in Aim 2 (EEG, MEG, and MRI at the MRN). Mood manipulation will occur during EEG assessment, immediately prior to task performance.

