In Aim 1a, a mood induction procedure will be utilized in control (non-depressed participants only), similar to Mayberg et al. (1999b), based on the suggestions of Martin (1990). The procedure consists of a combination of re-experiencing an autobiographical sad personal event while listening to their choice of one of four sad music selections commonly used in mood induction (Ramel et al., 2007). Visual analogue scale ratings will assess momentary sadness prior to, following, and at subsequent time points around the mood induction procedure. A positive mood repair procedure will be used after the tasks in order to ensure that the participant experiences the sadness experience as transitory.

In **Aim 1b**, emotional images similar to positive and negative International Affective Picture Set (IAPS: Bradley & Lang, 1999) images or emotional faces (Ekman, 1992) will be used to alter the emotional information of stimuli or reinforcements. Aim 1b will contain both control and depressed participants.

The three-to-six month followup phone interview will consist of a verbal or online (via COINS) completion of a Beck Depression Inventory. If participants consent to a follow-up phone interview, they will be contacted by research staff and asked if they are still interested in completing the survey. If they agree, a time and method for completion (verbal or online) will be setup. It should take 5-12 minutes to complete the BDI.

9) **List of Appendices**

Demographics form (age, gender, race, etc.)
Handedness questionnaire
Beck Depression Inventory (BDI)
Diagnosis information (SCID)
Mood and Anxiety Symptoms Questionnaire (MASQ)
Behavioral Inhibition / Activation Scales (BIS/BAS)
Snaith-Hamilton Pleasure Scale (SHAPS)
Dimensional Anhedonia Rating Scale (DARS)
Apathy-Motivation Index (AMI)

10) **Data and Specimen Banking**

No specimens will be banked as part of this protocol. Participants will be given the option of having their data stored in the MRN Data Repository (see HRRC# 06-387, PI: [name]).

11) **Data Management**

Consent Forms/HIPAA Authorizations: Signed consent forms are stored in a locked cabinet in a locked office in Logan hall on UNM main campus.

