Statistical Analysis Plan

NCT03856177

03/15/2023

In relation to ERP data, we first aimed to conceptually replicate and extend findings by Foti & Hajcak (2010) by assessing whether the RewP was affected by mood. An independent-samples t-test was conducted between mood manipulation groups (sad vs. neutral) to test whether sad mood could relatively reduce the RewP. The RewP was quantified as a reward-specific ERP component at electrode site FCz and amplitude was measured as the average amplitude within a 200–350ms time window. The electrode site and time window were decided a priori based on previous work utilizing the probabilistic selection task to investigate the RewP ([name] et al., 2019). Data were analyzed using the Jamovi toolkit in R. There was no adjustment for multiple comparisons correction.

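### Does the missing Aim 1 definition of non-depressed undermine the SAP's sad versus neutral comparison?

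*Protocol*

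**What the plan says.** Section 4 of the protocol (Inclusion and Exclusion Criteria) opens the relevant bullet with "In Aim 2, participants will need to either meet criteria for Major Depressive Disorder via a Structured Clinical Interview for the DSM-5 (SCID") and continues "or have an absence of symptoms to qualify as a control". Both halves apply to Aim 2 only.

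For Aim 1 the population is described in words. The Objectives expect that "a sadness manipulation in healthy controls should diminish the RewP". Section 8 says that in Aim 1a "a mood induction procedure will be utilized in control (non-depressed participants only"). Aim 1b is to include both groups. Neither section gives an instrument, cut-off or interview for these labels.

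Section 4 also excludes "Any other Axis 1 disorder (unless secondary to depression for depressed group in Aim 2"), and any comorbidity that the investigator thinks would compromise participation. The questionnaire list in section 8 includes the BDI and "Diagnosis information (SCID") without tying either to an aim. It says participants complete one or more of the instruments and gives no timing.

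The SAP describes a single comparison: "An independent-samples t-test was conducted between mood manipulation groups (sad vs. neutral) to test whether sad mood could relatively reduce the RewP". It has no symptom covariate, restriction or stratum.

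**The concern.** The same word, control, has a stated rule in Aim 2 and none in Aim 1. Someone with depressive symptoms short of MDD fits neither Aim 2 group, but fails no written depression criterion for Aim 1 and could be counted as an Aim 1a control.

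This would matter because the Background, in reviewing the reliability of the RewP, cites "including reliable diminution due to depressive symptoms". The characteristic left undefined is therefore one that the protocol itself links to a lower endpoint, in the direction of the hypothesis. If symptomatic people were more common in the sad group, an unadjusted t-test could not separate their lower RewP from an effect of the induction. Even with balanced groups, the result would describe a broader population than the healthy controls named in the Objectives.

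**Working it through.** **What the documents supply.** They give no alpha, power, effect size, SD or group size for the sad versus neutral test, so there is no figure of the plan's own to reproduce. Section 25 gives 150 controls and 50 depressed participants for Aim 1. The split of controls between Aims 1a and 1b is not stated. If all 150 were in Aim 1a and divided equally, each group would have 150/2 = 75, which is the ceiling. I use 25, 50 and 75 per group. Every other input below is an assumption.

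**Step 1: what is actually missing.** Section 8 restricts Aim 1a to non-depressed people, so a restriction exists. What is unwritten is how it was applied. In the Axis 1 exclusion, the word other reads most naturally as other than MDD, so other depressive diagnoses are arguably excluded too. What remains is mainly subthreshold symptoms, plus any MDD missed if no interview was done.

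**Step 2: who enters the test.** The SAP names no aim. Mood induction appears only in Aim 1a, so the link is a reasonable inference. The 50 depressed participants cannot be in Aim 1a, and the SAP has no Aim 1b contrast. At most 150 people are affected.

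**Step 3: random allocation, symptomatic people respond like others.** Expected bias is zero, and symptoms only add variance. With symptomatic share f and RewP deficit g (in SD units), the SD becomes √(1 + f(1−f)g²). For f = 0.30 and g = 0.5 this is √(1 + 0.21 × 0.25) = √1.0525 = 1.026. With a true effect of 0.5 SD, power is approximately Φ(0.5·√(n/2)/SD − 1.96):

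| n per group | no symptomatic people | 30% symptomatic |
|---|---|---|
| 25 | 42.4% | 40.6% |
| 50 | 70.5% | 68.3% |
| 75 | 86.5% | 84.7% |

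The loss is about 2 percentage points.

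**Step 4: random allocation, symptomatic people do not respond at all.** The mean effect becomes 0.5(1−f). For f from 10% to 30%, power falls to 35.0–22.5% (n = 25), 60.5–40.0% (n = 50) and 77.8–55.1% (n = 75). The test is still valid: it estimates the average effect in the people enrolled.

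**Step 5: unequal groups.** The spurious difference is the imbalance in symptomatic share times the deficit: 0.05 × 0.3 = 0.015 SD up to 0.20 × 0.8 = 0.16 SD, with a middle case of 0.10 × 0.5 = 0.05 SD. The rejection rate of a two-sided 5% t-test when the induction has no effect comes from the noncentral t, with noncentrality d·√(n/2) and 2n − 2 degrees of freedom:

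| n per group | d = 0.015 | d = 0.05 | d = 0.16 |
|---|---|---|---|
| 25 | 5.0% | 5.3% | 8.6% |
| 50 | 5.1% | 5.7% | 12.4% |
| 75 | 5.1% | 6.1% | 16.4% |

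**Step 6: could chance produce the worst case?** At 75 per group, the standard error of the difference in symptomatic share is √(2p(1−p)/75). For p = 0.10 it is 0.049 and for p = 0.30 it is 0.075. A 20-point gap is then 0.20/0.049 = 4.1 or 0.20/0.075 = 2.7 standard errors. Under random allocation it is very unlikely, so the right-hand column needs a systematic difference between groups.

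**The case for a change.** The strongest case for a change is that the undefined characteristic is one the protocol says lowers the endpoint, that the SAP ignores it, and that the remedy is cheap: a BDI-adjusted sensitivity model, an analysis restricted to symptom-free participants, and baseline BDI by mood group. The reading of the text behind this is correct. It is also true that neither document states how people were assigned to sad or neutral, so balance is not guaranteed on paper, and that the dilution in step 4 would survive randomisation.

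Less of this stands as a reason to alter the plan:

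- The false-positive figures measure the effect of non-random allocation. If allocation were non-random, a symptom-free entry rule would leave every other confounder in place.
- A BDI main-effect covariate would not undo the dilution in step 4. Its gain is modest: an assumed BDI–RewP correlation of 0.2 to 0.4 raises power at 50 per group from 70.5% to 72.3–77.9%.
- The restricted analysis would borrow Aim 2's symptom-free standard, which itself has no cut-off.
- Any BDI analysis needs a score taken before the induction, and section 8 does not guarantee one.
- The SAP is written in the past tense, so added models might well be post hoc.
- The study cited for symptom-related reduction concerns childhood and adolescence according to its title in the reference list, whereas participants here are 18 to 55. It makes an effect plausible in adults with mild symptoms but does not give its size.

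**Conclusion.** The observation about the text is right, but it is missing detail rather than a flaw in the analysis. Followed as written, in people judged non-depressed, the t-test is not shown to give a wrong answer. Under random allocation the consequences are how the population is described and some loss of power: about 2 percentage points with 30% symptomatic, and more only if those people do not respond to the induction. Bias needs systematic imbalance, for which the documents give no evidence; the middle case gives a false-positive rate of 5.3–6.1% against a nominal 5%. Nor do the documents show that anyone symptomatic was enrolled.

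These sizes rest on assumed shares, deficits, effect size and group sizes. The conclusion that the test is valid rests on random allocation, which is a separate unstated point. Analysts can be expected to fill the gap in the ordinary course of reporting, by saying how non-depressed status was established and describing the baseline BDI where it was collected. The Aim 1b labels are open in the same way, but no SAP test depends on them.

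### Does the SAP's sad-versus-neutral test lack a basis in the protocol, which describes only the sad induction?

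*Protocol*

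**What the plan says.** The protocol's Objectives predict, under Aim 1, that making healthy controls sad will lower the RewP. Section 8 (Study Methods, Mood and Emotion Manipulations) confines manipulation to that aim: "Mood and emotion manipulation procedures will only be used in Aim 1 (EEG in Logan Hall) and not in Aim 2". For Aim 1a, "a mood induction procedure will be utilized in control (non-depressed participants only", and the procedure combines "re-experiencing an autobiographical sad personal event while listening to their choice of one of four sad music selections". Two features surround it. The first is repeated self-rating: "Visual analogue scale ratings will assess momentary sadness prior to, following, and at subsequent time points around the mood induction procedure". The second is a step that lifts mood again once the tasks are finished, so that the induced sadness does not last. Aim 1b uses emotional images or faces, and "Aim 1b will contain both control and depressed participants".

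Section 25 plans 50 depressed participants and 150 controls for Aim 1, and 50 of each for Aim 2. It does not divide the 150 controls between Aims 1a and 1b or between mood groups. Section 7 lists no endpoints, and the statistical paragraph in Section 11 names general families of methods only.

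The SAP, dated 03/15/2023, is a single paragraph in the past tense. It says "we first aimed to conceptually replicate and extend findings by" a published study, and then: "An independent-samples t-test was conducted between mood manipulation groups (sad vs. neutral". The outcome is mean amplitude at FCz from 200 to 350 ms. It gives no group sizes.

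**The concern.** A reader who moves from the SAP back to the protocol looks for the neutral group and does not find it. The Aim 1a paragraph describes one procedure, and it is sad throughout. Nothing else in Section 8 fills the role. Mood repair comes after the tasks, so it cannot be a comparator for a RewP recorded during them. Aim 1b changes the emotional content of stimuli or reinforcements, which is not a neutral mood group.

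Three things would be at stake.

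- **Meaning of the contrast.** A matched neutral induction isolates sadness. A group with no induction would also differ in recall, music and session length.
- **Causal standing.** A randomised contrast supports a causal reading directly. A non-randomised one does not.
- **Precision.** Without group sizes, the documents do not show what effect a non-significant result would exclude.

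Because this is the only test the SAP specifies, a gap here draws more attention than it would in a longer plan.

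**Working it through.** **Step 1. What the protocol supplies for the test.**

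| Element of the SAP test | In the protocol? |
|---|---|
| Hypothesis: sadness lowers the RewP in controls | Yes, Objectives, Aim 1 |
| Population: non-depressed participants | Yes, Section 8, Aim 1a |
| Task and signal: feedback-locked EEG in the probabilistic selection task | Yes, Section 8, Tasks |
| Sad condition | Yes, Section 8, Aim 1a |
| Neutral condition | Not described |
| Method of assignment | Not described |
| Number per mood group | Not described |

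Four of the seven elements are present. The three that are absent all concern the comparator.

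**Step 2. Conflict or silence?** A conflict would need the protocol to say that there is one group only, that there is no comparator, or that the RewP is compared before and after induction. It says none of these. The repeated measurements in the Aim 1a paragraph are sadness ratings, not RewP recordings. The SAP therefore adds a condition on which the protocol is silent.

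**Step 3. Enrolment.** Inputs are from Section 25: 50 + 150 + 50 + 50 = 300, which reproduces the stated total. If the neutral group was drawn from the Aim 1 controls, the equal-split ceiling is 150/2 = 75 per group, and it is lower if Aim 1b used different controls. That ceiling is conditional. If the neutral group had received no procedure at all, the 50 Aim 2 controls, who also do the selection task with concurrent EEG, could in principle have served. The SAP's reference to manipulation groups makes that unlikely.

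**Step 4. Precision, as illustration only.** Assumptions: two-sided 5% level, 80% power, and the group sizes below, none of which the documents give.

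- 95% half-width in SD units = t(0.975, n1+n2−2) × √(1/n1 + 1/n2)
- Detectable difference from the noncentral t. The normal approximation (1.960 + 0.842) × √(1/n1 + 1/n2) serves as a check.

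| n1/n2 | √(1/n1+1/n2) | Half-width | Detectable difference | Normal check |
|---|---|---|---|---|
| 75/75 | 0.163 | 0.323 | 0.460 | 0.457 |
| 50/50 | 0.200 | 0.397 | 0.566 | 0.560 |
| 67/33 | 0.213 | 0.422 | 0.602 | 0.596 |
| 25/25 | 0.283 | 0.569 | 0.809 | 0.792 |

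These rows show how precision depends on a number that is not stated. They do not measure a defect. The SAP reports a test already carried out, so what a null result excludes follows from the observed interval and the actual group sizes.

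**Step 5. Would any answer change the analysis?**

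- *Random assignment to matched procedures:* the unadjusted t-test is appropriate as it stands.
- *Random assignment to sad induction or none:* the t-test is still valid, and only the interpretation widens to the whole induction package.
- *Non-random assignment:* the same t-test still describes the group difference, but the contrast should be read as observational. Nothing in either document points to this case. An adjusted model would have limited value, because no RewP before induction is described and Section 8 asks participants for one or more of the listed questionnaires, not for all of them.

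**The case for a change.** The strongest case for a change is that this is the SAP's only inferential test and neither document says what the comparison group did. The protocol version is labelled 12.19.18 and the SAP came in 2023, so the supplied text does not show that the comparator was fixed in advance. The obvious rescues do not work: mood repair comes after the tasks, Aim 1b is a different manipulation, and the Aim 1a paragraph reads as complete, so redaction is not a likely explanation. A few sentences would close the gap at almost no cost.

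Most of this stands as description. The neutral procedure, the assignment and the group sizes are indeed absent from the supplied text. The sources cited for the induction could not be read and might describe a control condition, but that cannot be relied on.

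The step from omission to a needed change does not stand. Writing the facts down in 2023 or later would not show that they were set beforehand, and it would not alter the data or the test. A precaution against non-random assignment answers a problem for which there is no evidence, since the SAP's wording suggests conditions set by the experimenter. Nor does it help the case that the SAP's replicated study carries a year absent from the protocol's reference list. The documents cannot show whether the year is a slip, and the comparator does not depend on it.

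**Conclusion.** The observation is accurate but calls for no change to the plan. It is a gap in description that an analyst or reader fills in the ordinary way: two separate groups, both manipulated by the experimenter, one sad and one neutral, compared on one outcome at a fixed site and time window. The missing facts belong in the report of the result, where group sizes and the observed interval settle precision directly.

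The effect on the t-test is nil under random assignment, whether or not the neutral procedure was matched. If assignment was not random, the label on the contrast would change but the calculation would not, and the documents give no sign of that case. The range of 0.32 to 0.57 SD for the half-width rests on assumed groups of 75 down to 25, with 75 a ceiling only if the neutral group came from the Aim 1 controls and the split was equal. It illustrates an unstated number and is not evidence of bias or error.
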